4.1. Inclusion Criteria

Subjects must meet all of the following inclusion criteria to be eligible for enrollment into the study:

- 1. Evidence of a personally signed and dated ICD indicating that the parent(s)/legal guardian has been informed of all pertinent aspects of the study.
- 2. Subject whose caregiver is willing and able to comply with scheduled visits, treatment plan, and other study procedures. The subject's caregiver must be able to be reached by telephone for the duration of the study.
- 3. Aged 6 weeks (42 days) to <6 years at the time of consent.
 - Cohort 1: Subjects 6 weeks to 2 months (42 to 56 days) of age;
 - Cohort 2: Subjects 7 months (210 days) to <12 months (< 365 days) of age;
 - Cohort 3: Subjects \geq 1 year to <2 years of age;
 - Cohort 4: Subjects ≥ 2 years to ≤ 6 years of age.
- 4. Healthy infants and children as determined by medical history, physical examination, and judgment of the investigator.

4.2. Exclusion Criteria

Subjects with any of the following characteristics/conditions will not be included in the study:

- 1. Infant or child who is a family member of:
 - Investigator site staff members directly involved in the conduct of the study;
 - Site staff members otherwise supervised by the investigator;
 - Pfizer employees directly involved in the conduct of the study.
- 2. Participation in other studies involving investigational drug(s)/vaccine(s) since birth (Cohort 1 only) or in the 6 months prior to study entry (Cohorts 2, 3, and 4) and/or during study participation.
- 3. Other acute or chronic medical or psychiatric condition, including recent laboratory abnormality, that may increase the risk associated with study participation or investigational product administration or may interfere with the interpretation of study results and, in the judgment of the investigator, would make the subject inappropriate for entry into this study.
- 4. Previous vaccination with licensed or investigational pneumococcal vaccine.
- 5. Previous vaccination with licensed or investigational Hib vaccine.
- 6. A previous anaphylactic reaction to any vaccine or vaccine-related component.
- 7. Contraindication to vaccination with pneumococcal or Hib vaccines (refer to local package insert).
- 8. Bleeding diathesis or condition associated with prolonged bleeding time that would contraindicate intramuscular injection.
- 9. Known or suspected immune deficiency or suppression.
- 10. History of culture-proven invasive disease caused by S pneumoniae.
- 11. Major known congenital malformation or serious chronic disorder.
- 12. Significant neurological disorder or history of seizure, including febrile seizure, or significant stable or evolving disorders such as cerebral palsy, encephalopathy, hydrocephalus, or other significant disorders. Does not include resolving syndromes due to birth trauma such as Erb palsy.
- 13. Receipt of blood products or gamma globulin. Hepatitis B immunoglobulin may be given.

4.3. Criteria for Temporarily Delaying Vaccine Administration

The following conditions are temporary or self-limiting and a subject may be randomized and/or vaccinated once the condition(s) has resolved:

- 1. Current febrile illness (axillary temperature greater than or equal to 37.1°C [98.8°F]) or other acute illness within 48 hours before investigational product administration. Investigational product administration need not be delayed in the event of an afebrile illness if, according to local vaccination practice and the investigator's judgment, the subject should be vaccinated.
- 2. Subject has received any vaccine within the previous 4 days, except for bacille Calmette Guérin (BCG) vaccine and oral vaccines, which are allowed at any time.
- 3. Subject has received systemic antibiotic therapy within the last 5 days.

4.4. Sponsor's Qualified Medical Personnel

The contact information for the sponsor's appropriately qualified medical personnel for the study is documented in the study contact list located in the supporting study documentation.

To facilitate access to appropriately qualified medical personnel on study-related medical questions or problems, subjects are provided with a contact card. The contact card contains, at a minimum, protocol and investigational product identifiers, subject study numbers, contact information for the investigator site, and contact details for a contact center in the event that the investigator site staff cannot be reached to provide advice on a medical question or problem originating from another healthcare professional not involved in the subject's participation in the study. The contact number can also be used by investigator staff if they are seeking advice on medical questions or problems; however, it should be used only in the event that the established communication pathways between the investigator site and the study team are not available. It is therefore intended to augment, but not replace, the established communication pathways between the investigator site and the study team for advice on medical questions or problems that may arise during the study. The contact number is not intended for use by the subject directly, and if a subject calls that number, he or she will be directed back to the investigator site.

5. INVESTIGATIONAL PRODUCTS

For the purposes of this study, and per International Council for Harmonisation (ICH) guidelines, investigational product is defined as a pharmaceutical form of an active ingredient or placebo being tested or used as a reference/comparator in a clinical trial, including a product with a marketing authorization when used or assembled (formulated or packaged) in a way different from the approved form, or when used for an unapproved indication, or when used to gain further information about an approved use (ICH E6 1.33).

This study is open-label and subjects will receive the investigational products, 13vPnC or Hib vaccine (comparator).

For this study, the investigational product(s) are 13vPnC and Hib vaccine.

5.1. Allocation to Treatment

Subjects in cohort 1 will receive 13vPnC.

Subjects in Cohort 2, 3 or 4 will be randomized in a 2:1 ratio to receive one of the following investigational products:

- o 13vPnC
- Hib vaccine (comparator)

The investigator's knowledge of the treatment should not influence the decision to enroll a particular subject or affect the order in which subjects are enrolled.

Allocation of subjects to vaccine groups will proceed through the use of an interactive response technology (IRT) system or equivalent system.

The study-specific IRT reference manual will provide the contact information and further details on the use of the IRT system or equivalent system.

5.2. Subject Compliance

All doses of investigational product will be administered by the appropriately designated study staff at the investigator site.

5.3. Investigational Product Supplies

5.3.1. Formulation and Packaging

13vPnC and Hib vaccine will be commercially available vaccines packed and labeled in accordance with applicable legal and regulatory requirements. 13vPnC and Hib vaccine will be sourced locally by the site according to local regulations.

This is an open-label study, as the investigational products have different appearances.

5.3.1.1. 13-valent Pneumococcal Conjugate Vaccine

Commercially available 13vPnC will be provided in accordance with local regulations.

13vPnC contains saccharides from pneumococcal serotypes 1, 3, 4, 5, 6A, 6B, 7F, 9V, 14, 18C, 19A, 19F, and 23F individually conjugated to cross-reactive material 197 (CRM₁₉₇). The vaccine is formulated to contain 2.2 μ g of each saccharide, except for 4.4 μ g of 6B, per 0.5-mL dose. The final formulation contains 5 mM succinate buffer, with 0.125 mg of aluminum as aluminum phosphate per 0.5-mL dose. Polysorbate 80 at 0.02% is added as an excipient.

The SRSD for 13vPnC is the Investigator Brochure.

5.3.1.2. Haemophilus influenzae Type b Vaccine

A commercially available Hib vaccine will be provided for vaccination of subjects in Cohorts 2, 3 or 4 randomized to the Hib group. The Hib vaccine will be sourced by the sites in accordance with local regulations.

The SRSD for Hib vaccine is the local package insert.

5.3.2. Preparation and Dispensing

See the Investigational Product Manual (IP manual), package insert, or equivalent for instructions on how to prepare the investigational product for administration. Investigational product should be prepared and dispensed by an appropriately qualified and experienced member of the study staff (eg, physician, nurse, physician's assistant, nurse practitioner, pharmacy assistant/technician, or pharmacist) as allowed by local, state, and institutional guidance.

5.3.3. Administration

Investigational product administration will be documented in the case report form (CRF).

13vPnC or Hib vaccine should be administered intramuscularly into a left limb (left anterolateral thigh muscle or deltoid of the left arm) in accordance with the local package insert at the vaccination visits, see Table 5.

Any concomitant vaccines required by local recommendations and permitted by the protocol may be administered concomitantly, but must be given in a different limb.

Standard vaccination practices must be observed and vaccine must not be injected into blood vessels. Appropriate medication and other supportive measures for management of an acute hypersensitivity reaction should be available in accordance with local guidelines for standard immunization practices.

Administration of investigational products should be performed by an appropriately qualified, Good Clinical Practice (GCP)-trained, and vaccine-experienced member of the study staff (eg, physician, nurse, physician's assistant, nurse practitioner, pharmacist, or medical assistant) as allowed by local, state, and institutional guidance.

Investigational product administration details will be recorded on the CRF.

5.4. Investigational Product Storage

Upon receipt at the study site, 13vPnC and the Hib vaccine should be immediately transferred to a $+2^{\circ}C$ to $+8^{\circ}C$ temperature-monitored refrigerator for storage. 13vPnC and the Hib vaccine must be stored in accordance with the product label. The vaccines must not be frozen.

The investigator or an approved representative, eg, pharmacist, will ensure that all investigational products, 13vPnC and Hib vaccine, are stored in a secured area with

controlled access under required storage conditions and in accordance with applicable regulatory requirements.

Investigational products should be stored in their original containers and in accordance with the labels. Any storage conditions stated in the SRSD will be superseded by the storage conditions stated on the product label.

Site systems must be capable of measuring and documenting (for example, via a log), at a minimum, daily minimum and maximum temperatures for all site storage locations (as applicable, including frozen, refrigerated, and/or room-temperature products). This should be captured from the time of investigational product receipt throughout the study. Even for continuous-monitoring systems, a log or site procedure that ensures active evaluation for excursions should be available. The intent is to ensure that the minimum and maximum temperature is checked each business day to confirm that no excursion occurred since the last evaluation and to provide the site with the capability to store or view the minimum/maximum temperature for all non-working days upon return to normal operations. The operation of the temperature monitoring device and storage unit (for example, refrigerator), as applicable, should be regularly inspected to ensure they are maintained in working order.

Any excursions from the product label storage conditions should be reported to Pfizer upon discovery. The site should actively pursue options for returning the product to the storage conditions described in the labeling, as soon as possible. Deviations from the storage requirements, including any actions taken, must be documented and reported to Pfizer.

Receipt of materials, door opening and closing, and other routine handling operations where the products are briefly out of the temperature range described in the labeling are not considered excursions.

Once an excursion is identified, the investigational product must be quarantined and not used until Pfizer provides permission to use the investigational product. It will not be considered a protocol deviation if Pfizer approves the use of the investigational product after the temperature excursion. Use of the investigational product prior to Pfizer approval will be considered a protocol deviation. Specific details regarding information the site should report for each excursion will be provided to the site.

5.5. Investigational Product Accountability

The investigator site must maintain adequate records documenting the receipt, use, loss, or other disposition of the investigational product supplies. All investigational products will be accounted for using a drug accountability form/record.

5.5.1. Destruction of Investigational Product Supplies

The sponsor or designee will provide guidance on the destruction of unused investigational product (eg, at the site). If destruction is authorized to take place at the investigator site, the investigator must ensure that the materials are destroyed in compliance with applicable environmental regulations, institutional policy, and any special instructions provided by Pfizer, and all destruction must be adequately documented.

5.6. Concomitant Treatment(s)

The name and date of administration of any nonstudy vaccines given from the time of signing the consent form until 6 months after the last vaccination visit will be recorded in the CRF. Other medications (except for antipyretic medication use) will not be recorded in the CRF. Antipyretic medication taken will be reported in the subject's e-diary and stop date recorded in the e-diary/CRF (as part of the symptoms resolved dates CRF).

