a. Subjects in Cohort 2 randomized to Hib vaccine will not receive a vaccination at Visit 3. These subjects may receive a third dose of Hib vaccine according to local practice or national recommendations, at the discretion of the investigator.

b. Subjects in Cohort 3 randomized to Hib vaccine will not receive a vaccination at Visit 2.

STATISTICAL ANALYSIS

All of the analyses will be summarized for each cohort separately.

Immunogenicity Analysis Populations

An evaluable immunogenicity population and an all-available immunogenicity population will be defined for the immunogenicity analyses separately. The evaluable immunogenicity population will be the primary population for the immunogenicity analyses.

Safety Analysis

The safety population will be defined for safety analysis. The safety population will include all subjects who receive at least 1 dose of an investigational product.

Analysis Timing:

The primary analysis will be performed when the following data are available:

- IgG immunogenicity data 1 month after the infant series in Cohort 1;
- IgG immunogenicity data 1 month after the last dose of 13vPnC in Cohorts 2, 3, 4;
- Safety data up to 6 months after the last study vaccination for Cohorts 2, 3 and 4.

SCHEDULE OF ACTIVITIES

The schedule of activities table provides an overview of the protocol visits and procedures. Refer to the Study Procedures and Assessments sections of the protocol for detailed information on each procedure and assessment required for compliance with the protocol. The investigator may schedule visits (unplanned visits) in addition to those listed on the schedule of activities table, in order to conduct evaluations or assessments required to protect the well-being of the subject.

Visit Number	1	2	3	4	5	6	7	8 to 11
Visit Description	Vaccination	Vaccination	Vaccination	Post-	Vaccination	Post-Toddler	6-Month	Persistence
	1	2	3	Infant	4	Dose Visit	Follow-up	Blood Draws ^a
				Dose			Telephone	
x 74 4, xx 74 x	10 1 51	10 / 50	42 / 50	Visit	265 1 155	00 / 10 D	Contact	
Visit Window	42 to 56	42 to 70	42 to 70	28 to 42	365 to 455	28 to 42 Days	168 to 196 Days	Annually After
	Days of Age	Days After Visit 1	Days Alter Visit 2	Days	Days	After visit 5	Alter Last Study	VISIT 5
		v Isit I	v 1810 2	Visit 3	of Age		vaccination	
Informed consent	Х							
Review inclusion/exclusion criteria	Х							
Demography, medical history, and	Х							
physical examination								
Record nonstudy vaccines	Х	Х	Х	Х	Х	Х	Х	

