5.6.5. Prohibited Vaccines and Medications

No pneumococcal vaccines (licensed or investigational) other than those described in this study may be given prior to or during the study.

Local anesthetic cream should not be used at the site of investigational product administration.

Prophylactic use of antipyretic and other pain medications to prevent symptoms that might occur as a result of investigational product administration should be discouraged; however, it is recognized that use of antipyretic medication is a matter of parental choice and local clinical practice.

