6.1.7. Cohort 1: Visit 7, 6-Month Follow-up (168 to 196 Days After the Last Study Vaccination)

- Contact the subject's caregiver by telephone to inquire about SAEs or newly diagnosed chronic medical conditions. This may be a clinic visit if preferred by the caregiver.
- Record any nonstudy vaccinations.
- Ensure that the subject continues to be eligible for the study; refer to Subject Withdrawal section of the protocol.
- The investigator or an authorized designee completes the CRF.

6.1.8. Cohort 1: Visit 8, Persistence Blood Draw Visit (2 Years of Age to 2 Years and 28 Days of Age)

- Ensure that the subject continues to be eligible for the study; refer to Subject Withdrawal section of the protocol.
- Collect a blood sample (approximately 5 mL). Blood must be drawn from peripheral veins (eg, arm, foot, or scalp veins). Drawing blood from central veins (eg, jugular or femoral veins), which may increase the risk associated with study participation, is not permitted.
- Any AEs that occur within 48 hours after the blood draw should be recorded in the source documents and in the AE section of the CRF.
- Schedule an appointment with the caregiver for the next visit.
- The investigator or an authorized designee completes the CRF and updates the investigational product accountability records.
- Ask the caregiver to contact the investigator or other site staff if the subject reports any AEs that occur within 48 hours after the blood draw.

6.1.9. Cohort 1: Visit 9, Persistence Blood Draw Visit (3 Years of Age to 3 Years and 28 Days of Age)

- Ensure that the subject continues to be eligible for the study; refer to Subject Withdrawal section of the protocol.
- Collect a blood sample (approximately 5 mL). Blood must be drawn from peripheral veins (eg, arm, foot, or scalp veins). Drawing blood from central veins (eg, jugular or femoral veins), which may increase the risk associated with study participation, is not permitted.
- Any AEs that occur within 48 hours after the blood draw should be recorded in the source documents and in the AE section of the CRF
- Schedule an appointment with the caregiver for the next visit.
- The investigator or an authorized designee completes the CRF and updates the investigational product accountability records.
- Ask the caregiver to contact the investigator or other site staff if the subject reports any AEs that occur within 48 hours after the blood draw.

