6.1.10. Cohort 1: Visit 10, Persistence Blood Draw Visit (4 Years of Age to 4 Years and 28 Days of Age)

- Ensure that the subject continues to be eligible for the study; refer to Subject Withdrawal section of the protocol.
- Collect a blood sample (approximately 5 mL). Blood must be drawn from peripheral veins (eg, arm, foot, or scalp veins). Drawing blood from central veins (eg, jugular or femoral veins), which may increase the risk associated with study participation, is not permitted.
- Any AEs that occur within 48 hours after the blood draw should be recorded in the source documents and in the AE section of the CRF.
- Schedule an appointment with the caregiver for the next visit.
- The investigator or an authorized designee completes the CRF and updates the investigational product accountability records.

• Ask the caregiver to contact the investigator or other site staff if the subject reports any AEs that occur within 48 hours after the blood draw.

6.1.11. Cohort 1: Visit 11, Persistence Blood Draw Visit (5 Years of Age to 5 Years and 28 Days of Age)

- Ensure that the subject continues to be eligible for the study; refer to Subject Withdrawal section of the protocol.
- Collect a blood sample (approximately 5 mL). Blood must be drawn from peripheral veins (eg, arm, foot, or scalp veins). Drawing blood from central veins (eg, jugular or femoral veins), which may increase the risk associated with study participation, is not permitted.
- Any AEs that occur within 48 hours after the blood draw should be recorded in the source documents and in the AE section of the CRF.
- Schedule an appointment with the caregiver for the next visit.
- The investigator or an authorized designee completes the CRF and updates the investigational product accountability records.
- Ask the caregiver to contact the investigator or other site staff if the subject reports any AEs that occur within 48 hours after the blood draw.

6.2. Cohort 2

6.2.1. Cohort 2: Visit 1, Vaccination 1 (7 Months [210 Days] to <12 Months [<365 Days] of Age)

- Obtained informed consent from the subject's parent(s)/legal guardian(s) prior to performing any protocol-required procedures.
- Obtain and record the subject demography (including full date of birth, sex and race. The date of birth will be collected to critically evaluate the immune response and safety profile by age).
- Obtain and record the subject's medical history.

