6.6. Subject Withdrawal

Subjects may withdraw from the study at any time at the request of their parent(s)/legal guardian, or they may be withdrawn at any time at the discretion of the investigator or sponsor for safety (see also the Withdrawal From the Study Due to Adverse Events section) or behavioral reasons, or the inability of the subject to comply with the protocol-required schedule of study visits or procedures at a given study site.

If a subject does not return for a scheduled visit, every effort should be made to contact the subject's caregiver. All attempts to contact the subject and information received during contact attempts must be documented in the subject's medical record. In any circumstance, every effort should be made to document subject outcome, if possible. The investigator should inquire about the reason for withdrawal, request that the subject return for a final visit, if applicable, and follow up with the subject regarding any unresolved AEs.

If the subject withdraws from the study, and their parent(s)/legal guardian also withdraws consent for disclosure of future information, no further evaluations should be performed, and no additional data should be collected. The sponsor may retain and continue to use any data collected before such withdrawal of consent.

The decision to withdraw a subject from the study should be discussed with the sponsor's medical monitor.

When a decision has been made to discontinue further vaccination with the investigational product, the subject should, if possible, be followed for 6 months after the subject's final study vaccination before being permanently withdrawn from the study. In this period, every effort should be made to collect safety data and all data specified by the protocol including post-vaccination blood collection.

Eligibility criteria should be taken into consideration when determining if a subject should be withdrawn.

The following is a list of some examples, but not all, of the AEs that may warrant the withdrawal of a subject from the study unless there was an obvious alternative cause:

- Persistent, inconsolable screaming or crying for 3 or more hours within 48 hours after vaccination.
- Collapse or shock-like state (hypotonic-hyporesponsive episode) within 48 hours after vaccination.
- Temperature greater than or equal to 40.0°C (104.0°F) unexplained by another cause, within 48 hours after vaccination.
- Anaphylactic/anaphylactoid reaction, including shock.
- Encephalopathy.

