3.5.3.2. Concomitant Vaccines and Medication(s)

The name and date of administration of any nonstudy vaccines given from the time of signing the ICD until 6 months after the last vaccination visit will be recorded in the CRF. Other medications (except for antipyretic medication use) will not be recorded in the CRF. Antipyretic medication taken will be reported in the subject's e-diary and stop date recorded in the e-diary/CRF (as part of the symptoms resolved dates CRF).

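### In Cohort 1 nothing at Visits 8-11 prompts for or dates a non-study pneumococcal vaccine, so re-vaccination before a persistence draw may go undetected

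*Protocol*

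**What the plan says.** **Prohibition.** Protocol 5.6.5: "No pneumococcal vaccines (licensed or investigational) other than those described in this study may be given prior to or during the study". For Cohort 1 the study runs to the age-5 draw at Visit 11.

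**Recording.** Protocol 5.6 has the CRF take the name and date of "any nonstudy vaccines given from the time of signing the consent form until 6 months after the last vaccination visit will be recorded". SAP 3.5.3.2 sets the same limit: "any nonstudy vaccines given from the time of signing the ICD until 6 months after the last vaccination visit will be recorded". In Table 1 of the Schedule of Activities the row "Record nonstudy vaccines" is marked at Visits 1-7 and empty in the column for Visits 8 to 11. The step lists agree: Visit 7 (Protocol 6.1.7) has a recording step, and Visits 8-11 (6.1.8 to 6.1.11) have none.

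**What Visits 8-11 do contain.** Each begins with "Ensure that the subject continues to be eligible for the study; refer to Subject Withdrawal section of the protocol". Protocol 6.6 then says "Eligibility criteria should be taken into consideration when determining if a subject should be withdrawn", and exclusion criterion 4 in Protocol 4.2 is "Previous vaccination with licensed or investigational pneumococcal vaccine". The remaining steps cover the draw, AEs within 48 hours of it, scheduling and routine CRF completion.

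**Analysis.** SAP 6.2.1 reports all Cohort 1 time points in the evaluable and all-available populations. SAP 5.2.2 adds GMRs of Cohort 1 persistence samples against Cohort 2-4 prevaccination samples. SAP 4.1 defines Cohort 1 evaluability around the draws 27-56 days after dose 3 and after dose 4. SAP 7.2 cites receipt of a prohibited vaccine as an example of a major violation that removes a subject from the evaluable population, and has the deviation list updated before the final analysis.

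**The concern.** The prohibition lasts to age 5, while the data that would show a breach stop being collected before age 2. Persistence through 5 years of age is a secondary objective (Protocol 2) and answers a regulator's request (Protocol 1.2). A child given another pneumococcal vaccine between Visit 7 and a draw would contribute boosted rather than waning antibody. The error runs in one direction: persistence GMCs and GMTs would be too high. The GMRs in SAP 5.2.2 would be affected on one side only, because Cohorts 2-4 must be free of earlier pneumococcal vaccination at entry. Without capture, the sponsor could not show that the effect is negligible.

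**Working it through.** The plan gives no figure on this point to reproduce. The check is date arithmetic on the visit windows, followed by a scale calculation on stated assumptions.

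**Inputs.** Dose 4 at 365-455 days of age; Visit 7 at 168-196 days after dose 4; draws at ages 2, 3, 4 and 5 years, each with 28 days allowed (Protocol Table 1 and 6.1.5 to 6.1.11).

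**End of recording.** Earliest 365 + 168 = 533 days (17.5 months). Latest 455 + 196 = 651 days (21.4 months).

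**Unrecorded interval before the draw at age y.** Shortest 365.25y - 651; longest 365.25y + 28 - 533. As a share of the time since dose 4, the denominators are 365.25y - 455 and 365.25y + 28 - 365.

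| Draw | Unrecorded days | Share of time since dose 4 |
|---|---|---|
| Visit 8 (age 2) | 80-226 | 29-57% |
| Visit 9 (age 3) | 445-591 | 69-78% |
| Visit 10 (age 4) | 810-956 | 81-85% |
| Visit 11 (age 5) | 1175-1321 | 86-89% |

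Example, Visit 11: 1826.25 - 651 = 1175.25, and 1826.25 + 28 - 533 = 1321.25. These shares measure calendar time without capture. They do not measure bias.

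**Scale of a possible bias.** If a share c of children has levels k-fold higher at the draw, the geometric mean is multiplied by k^c. For example, c = 5% and k = 10 give 10^0.05 = 1.12. The documents give neither c nor k, so the useful question is what c would make the bias equal the half-width of the 95% CI on the log scale: c = t x SD / (sqrt(n) x ln k).

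The SDs are the Cohort 1 natural-log IgG values in Protocol Table 12, from 0.652 (serotype 4) to 1.275 (serotype 19F). Persistence SDs are not given, so using these is an assumption, and more so for OPA.

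- IgG, n = 100 assumed, t(99) = 1.984. Half-width 1.984 x 0.652 / 10 = 0.129 to 1.984 x 1.275 / 10 = 0.253, so the upper limit lies 14-29% above the GMC.
- k = 10 (ln 10 = 2.303): c = 5.6-11%.
- k = 4 (ln 4 = 1.386): c = 9-18%.
- k = 2 (ln 2 = 0.693): c = 19-37%.
- OPA, n = 50, t(49) = 2.010. Half-width 2.010 x 0.652 / 7.071 = 0.185 to 2.010 x 1.275 / 7.071 = 0.362. For k = 10: c = about 8-16%.

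Below these shares the bias is smaller than the sampling error. Attrition by age 5 would reduce n and raise them.

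**The case against.** **The eligibility check could bring a case to light.** It refers to Protocol 6.6, which points to the eligibility criteria, and prior pneumococcal vaccination is one of the exclusions. This stands as an indirect route. It is still a general check that does not ask about vaccines and has nowhere to enter a name or date.

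**A reader might infer that a known case could never be placed before or after a draw.** The documents do not support that. The check is listed before the blood sample at each visit, so a case first found at Visit 9 after a clear Visit 8 check falls between the two draws. The ordering is rough and depends on the check having elicited the vaccination.

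**A reader might also infer that the SAP ignores such cases or contradicts itself.** It does neither. SAP 7.2 expressly gives receipt of a prohibited vaccine as an example of an excluding major violation, and the all-available set keeps every valid result because that is its purpose. What remains is narrower. The exclusion is by subject, so valid earlier draws may be lost with the affected ones. SAP 4.1 also does not clearly reach the age 2-5 draws: its post-toddler prohibited-vaccine criterion can be read as covering every draw after that dose, but the adjoining criterion fixes the draw at 27-56 days after vaccination 4.

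**Materiality is not shown.** The children have completed four doses, the breach is explicitly prohibited, and the regimen licensed in China ends at 15 months (Protocol 1.1, 1.2), before the unrecorded period starts. Protocol 1.2 does mention that a 23-valent polysaccharide vaccine has long been available, but gives no rate of use. This objection stands on size. It does not remove the capture gap.

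**Conclusion.** The gap in data capture is real, and Protocol 5.6, SAP 3.5.3.2, Table 1 and the Visit 8-11 step lists all show it. Between 80-226 days (Visit 8) and 1175-1321 days (Visit 11) before a persistence draw pass with no dedicated recording of non-study vaccines. Any undetected re-vaccination would bias the persistence GMCs and GMTs upward, and with them the GMRs that have Cohort 1 in the numerator.

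The size is unknown. On the assumed SDs, sample sizes and a 10-fold difference, 5.6-11% of children (IgG) or about 8-16% (OPA) would have to be affected for the bias to match the sampling error, so it may well be negligible. A reader might take the long unrecorded intervals as evidence that the persistence results are biased, or that the licensure comparison is at risk. Neither follows: no re-vaccination rate is given, the persistence results are descriptive, and the primary comparison uses the Cohort 1 draw after the infant series. This is a cheap improvement worth making, not a serious flaw.

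**What to change.** **Protocol and CRF.** At Visits 8-11 add one CRF item for the name and date of any non-study pneumococcal vaccine since the last contact. For visits already held, query vaccination records retrospectively. Extend the recording window in Protocol 5.6 and SAP 3.5.3.2 for Cohort 1 to match, and mark the Table 1 row accordingly.

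**SAP.** State that persistence draws taken after such a vaccine are excluded from the evaluable analysis while earlier draws are kept, with the planned all-available set as the sensitivity analysis. The prohibited-vaccine criterion of the infant-series and Cohorts 2-4 evaluable set has no bearing on these draws and needs no change.

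**Cost.** One more item at four scheduled visits, a minor protocol amendment and a short SAP addition. A few persistence samples may leave the evaluable analysis, and answers for past visits will depend on records or recall.
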